7.2 Contrast Reactions

Acute contrast reactions occur within minutes of administration of iodinated contrast. An estimated 3% of patient will experience mild contrast reaction that requires no treatment. However, moderate reactions such as bronchospasm or hypotension can occur in about 1 in 250 patients (0.4%) and about 1 in 1600 to 2500 (0.04-0.06%) of patients could experience a severe reaction²⁰. Treatment consist of administering medications directed at the specific cause of symptoms, such as bronchospasm with beta-2 agonist inhaler, while an airway or laryngeal edema should be treated with epinephrine. Antihistamine and/or corticosteroids could be administered if necessary. Delayed adverse reactions develop more than one hour after the procedure but within 7 days of IV contrast administration. It is mild in majority of cases and resolve without intervention. Non-specific symptoms range from Flu-like illness, arthralgia, aches and pains, parotitis, fever,

abdominal pain and headache. Treatment consists of antihistamine and/or corticosteroids. Severe cases may require a referral to a dermatologist.

7.3 Adverse Event Monitoring

Adverse event data collection and reporting, which are required as part of every clinical trial, are done to ensure the safety of subjects enrolled in the studies as well as those who will enroll in future studies using similar agents. Adverse events are assessed in a routine manner at scheduled times during a trial. Additionally, certain adverse events must be reported in an expedited manner to allow for optimal monitoring of subject safety and care.

All subjects experiencing an adverse event that is reported to Radiation Oncology discipline per study calendar, regardless of its relationship to study therapy, will be monitored until:

- The adverse event resolves or the symptoms or signs that constitute the adverse event return to baseline or is stable in the opinion of the investigator;
- There is a satisfactory explanation other than the study treatment for the changes observed; or
- Death.

7.3.1 Definitions

An adverse event is defined as any untoward or unfavorable medical occurrence in a human research study participant, including any abnormal sign (for example, abnormal physical exam, imaging finding or clinically significant laboratory finding), symptom, clinical event, or disease, temporally associated with the subject's participation in the research, whether or not it is considered related to the subject's participation in the research.

Adverse events encompass clinical, physical and psychological harms. Adverse events occur most commonly in the context of biomedical research, although on occasion, they can occur in the context of social and behavioral research. Adverse events may be expected or unexpected.

Acute Adverse Events

Adverse events occurring in the time period from the signing of the informed consent, through 1 month (+/- 10 days) post treatment planning procedure (CT angiogram) will be considered acute adverse events. Only kidney-specific adverse events will be followed should the subject receive more than the recommended dose of contrast, according to good medical practices. Acute adverse events, that are collected as specified within the protocol, will be assessed and reported as per below.

Late Adverse Events

Adverse effects occurring in the time period after the end of acute monitoring will be defined as late adverse events. Late adverse events will not be captured, assessed, graded or reported.

Severity

Adverse events will be graded by a numerical score according to the defined NCI Common Terminology Criteria for Adverse Events (NCI CTCAE) Version 5.0. Adverse events not specifically defined in the NCI CTCAE will be scored on the Adverse Event log according to the general guidelines provided by the NCI CTCAE and as outlined below.

- Grade 1: Mild

- Grade 2: Moderate
- Grade 3: Severe or medically significant but not immediately life threatening
- Grade 4: Life threatening consequences
- Grade 5: Death related to the adverse event

Serious Adverse Events

OHRP and UTSW HRPP define serious adverse events as those events, occurring at any dose, which meets any of the following criteria:

- Results in death
- Is life-threatening (places the subject at immediate risk of death from the event as it occurred)
- Results in inpatient hospitalization^{1,2} or prolongation of existing hospitalization
- Results in persistent or significant disability/incapacity
- Results in a congenital anomaly/birth defect
- Based upon appropriate medical judgment, may jeopardize the subject's health and may require medical or surgical intervention to prevent one of the other outcomes listed in this definition.

Note: A "Serious adverse event" is by definition an event that meets **any** of the above criteria. Serious adverse events may or may not be related to the research project. A serious adverse event determination does not require the event to be related to the research. That is, both events completely unrelated to the condition under study and events that are expected in the context of the condition under study may be serious adverse events, independent of relatedness to the study itself. As examples, a car accident requiring ≥24 hour inpatient admission to the hospital would be a serious adverse event for any research participant; likewise, in a study investigating end-stage cancer care, any hospitalization or death which occurs during the protocol-specified period of monitoring for adverse and serious adverse events would be a serious adverse event, even if the event observed is a primary clinical endpoint of the study.

¹Pre-planned hospitalizations or elective surgeries are not considered SAEs.

Note: If events occur during a pre-planned hospitalization or surgery, that prolongs the existing hospitalization, those events should be evaluated and/or reported as SAEs.

² NCI defines hospitalization for expedited AE reporting purposes as an inpatient hospital stay equal to or greater than 24 hours. Hospitalization is used as an indicator of the seriousness of the adverse event and should only be used for situations where the AE truly fits this definition and NOT for hospitalizations associated with less serious events. For example: a hospital visit where a patient is admitted for observation or minor treatment (e.g. hydration) and released in less than 24 hours. Furthermore, hospitalization for pharmacokinetic sampling is not an AE and therefore is not to be reported either as a routine AE or in an expedited report.

Unanticipated Problems Involving Risks to Subjects or Others (UPIRSOs):

The phrase "unanticipated problems involving risks to subjects or others" is found, but not defined in the HHS regulations at 45 CFR 46, and the FDA regulations at 21 CFR 56.108(b)(1) and 21 CFR 312.66. For device studies, part 812 uses the term unanticipated adverse device effect, which is defined in 21

CFR 812.3(s). Guidance from the regulatory agencies considers unanticipated problems to include any incident, experience, or outcome that meets ALL three (3) of the following criteria:

- Unexpected in terms of nature, severity or frequency given (a) the research procedures that are described in the protocol-related documents, such as the IRB-approved research protocol and informed consent document; and (b) the characteristics of the subject population being studied;
AND
- Related or possibly related to participation in the research (possibly related means there is a reasonable possibility that the incident, experience, or outcome may have been caused by the procedures involved in the research);
AND
- Suggests that the research places subjects or others at greater risk of harm (including physical, psychological, economic, or social harm) than was previously known or recognized. Note: According to OHRP, if the adverse event is serious, it would always suggest a greater risk of harm.

Follow-up

All adverse events, as specified in section 7.3, will be followed up according to good medical practices.

Kidney-specific adverse events will be followed up should the subject receive more than the recommended dose of contrast, according to good medical practices.

7.4 Steps to Determine If a Serious Adverse Event Requires Expedited Reporting to the SCCC DSMC

Step 1: Identify the type of adverse event using the NCI Common Terminology Criteria for Adverse Events (CTCAE v5).

Step 2: Grade the adverse event using the NCI CTCAE v5.

Step 3: Determine whether the adverse event is related to the protocol therapy. Attribution categories are as follows:

- Definite – The AE is *clearly related* to the study treatment.
- Probable – The AE is *likely related* to the study treatment.
- Possible – The AE *may be related* to the study treatment.
- Unlikely – The AE *may NOT be related* to the study treatment.
- Unrelated – The AE is *clearly NOT related* to the study treatment.

Note: This includes all events that occur within the acute adverse events reporting period as defined in section 7.3 and is attributed (possibly, probably, or definitely) to the treatment planning procedure (CT angiogram).

Step 4: Determine the prior experience of the adverse event. Expected events are those that have been previously identified as resulting from administration of the treatment. An adverse event is considered unexpected, for expedited reporting purposes only, when either the type of event or the severity of the event is not listed in:

- the current known adverse events listed in the Agent Information Section of this protocol (if applicable);
- the drug package insert (if applicable);
- the current Investigator's Brochure (if applicable)

- the Study Agent(s)/Therapy(ies) Background and Associated Known Toxicities section of this protocol

7.4.1 Reporting SAEs and UPIRSOs to the Simmons Comprehensive Cancer Center (SCCC) Data Safety Monitoring Committee (DSMC)

SAEs and UPIRSOs at all sites, which occur in research subjects on protocols for which the SCCC is the DSMC of record require reporting to the DSMC regardless of whether IRB reporting is required. All SAEs occurring during the protocol-specified monitoring period and all UPIRSOs should be submitted to the SCCC DSMC within 5 business days of the study team members' awareness of the event(s). In addition, for participating centers other than UTSW, local IRB guidance should be followed for local reporting of serious adverse events or unanticipated problems.

The UTSW study PI is responsible for ensuring SAEs/UPIRSOs are submitted to the SCCC DSMC Coordinator. This may be facilitated by the IIT project manager, study team, sub-site or other designee. Hardcopies or electronic versions of the eIRB Reportable Event report; FDA Form #3500A forms, or other sponsor forms, if applicable; and/or any other supporting documentation available should be submitted to the DSMC Coordinator. The DSMC Coordinator forwards the information onto the DSMC Chairman who determines if immediate action is required. Follow-up eIRB reports, and all subsequent SAE or UPIRSO documentation that is available are also submitted to the DSMC Chair who determines if further action is required. (See *Appendix III of the SCCC DSMC Plan for a template Serious Adverse Event Form which may be utilized*).

UPIRSOs must be promptly reported to the UTSW HRPP within 5 working days of study team awareness.

For research relying on a non-UT Southwestern IRB (external, central, or single IRB):

Investigators relying on an external IRB who are conducting research on behalf of UT Southwestern or its affiliates are responsible for submitting LOCAL UPIRSOs to the UT Southwestern IRB within 5 working days of study team awareness. Investigators must report to their relying IRB according to the relying IRB's policy. In addition, the external IRB's responses or determinations on these local events must be submitted to the UT Southwestern IRB within 10 working days of receipt.

Events NOT meeting UPIRSO criteria:

Events that do NOT meet UPIRSO criteria should be tracked, evaluated, summarized, and submitted to the UTSW HRPP/IRB at continuing review.

For more information on UTSW HRPP/IRB reportable event policy, see <https://www.utsouthwestern.edu/research/hrpp/quality-assurance/>

7.5 Stopping Rules

The study is designed to end if the rate of kidney injury from multiple contrast usage is higher than expected despite meeting the maximum recommended dose of contrast or an inability to consistently meet the recommended dose of contrast.

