4.3 Toxicities and Dosing Delays/Dose Modifications

The generally accepted safe upper limit total dose of iodinated contrast in one day is 225 mL of ISOVUE-370 for adults and 125 mL for children between the ages of 10 to 18. The amount of the administered contrast may be exceeded at the knowledgeable direction of the treating radiologists. All patients enrolled on the study will be assessed for the development of toxicity according to the Time and Events table (5.3) should the subject receive more than the recommended dose of contrast. Toxicity will be assessed according to the NCI Common Toxicity Criteria for Adverse Events (CTCAE), version 5.0. Contrast related allergic reactions will also be monitored per CTCAE criteria. Only AEs reported to Radiation Oncology discipline per study calendar will be captured and assessed.

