4.7 Duration of Follow Up

Nearly all the information needed for the protocol will be collected on the day of the procedure. Only AEs reported to Radiation Oncology discipline per study calendar will be captured and assessed. No follow up of AVM outcome is assessed as part of this protocol.

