5.3 Time and Events Table

	Pre-study ¹	Day 0	1 Week (-3 days, +7 days)	1 Month (+/- 10 days)
Informed Consent	X			
History and PE	X			
Serum Creatinine ²	X		X	X
Interventional Cerebral Arteriography		X		
CT Angiogram		X		
Adverse Event Assessment		X ³	X ³	X ³

1 – All screening procedures must be performed within 90 days prior to registration unless otherwise stated

2 – Within 30 days of SRS procedure

3 – Only if subject receives more than the recommended dose of contrast

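### The kidney-injury limb of the stopping rule mainly concerns subjects within the contrast limit, but scheduled AE assessment is restricted to subjects above it

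*Combined protocol and SAP*

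**What the plan says.** Section 7.5 has two triggers in one sentence. The first applies when "the rate of kidney injury from multiple contrast usage is higher than expected despite meeting the maximum recommended dose of contrast". The second is failure to keep consistently to the recommended dose.

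The AE provisions carry a different condition:

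- Section 4.3 assesses toxicity "according to the Time and Events table (5.3) should the subject receive more than the recommended dose of contrast".
- In the Time and Events Table (5.3), the AE assessment row is marked at Day 0, 1 week and 1 month. Each mark carries footnote 3: "Only if subject receives more than the recommended dose of contrast".
- Section 7.3.1, under acute adverse events: "Only kidney-specific adverse events will be followed should the subject receive more than the recommended dose of contrast".
- Section 7.3.1, under follow-up: "Kidney-specific adverse events will be followed up should the subject receive more than the recommended dose of contrast, according to good medical practices".

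Other provisions carry no dose condition. Sections 4.5, 5.2, 5.3 and 6.2 schedule serum creatinine at 1 week and 1 month for every subject. Section 9.3 puts the frequency and severity of renal toxicity into six-monthly interim reports, and 10.5 makes those reports the basis of toxicity review. Section 7.4.1 sends every serious adverse event in the monitoring period to the DSMC.

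**The concern.** A rule about injury in subjects who kept to the dose should draw on events recorded in those subjects. Here the dedicated AE assessment is scheduled for the other group. Section 4.6 intends the CT angiogram to stay within the contrast limits, so the group without scheduled AE assessment should be most or all of the 14 subjects.

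The kind of event matters too. Section 1.3 expects contrast nephropathy to appear, in the great majority of cases, as a temporary creatinine rise. Such a rise is usually not serious, so the serious-event route would not normally pick it up, yet it is the main event a renal stopping rule would count. A rise that is not recorded as an AE also falls outside the DSMC's quarterly AE review (10.5). Its scheduled review is then the six-monthly toxicity review.

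**Working it through.** The plan gives no figure to reproduce on this point: 7.5 states no expected rate, no definition of kidney injury and no number of cases that stops the study. The check is a comparison of texts, with some small sums.

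**1. Whom does 7.5 concern?** Exceeding the dose has its own limb, so meeting the dose in the first limb means staying within it. The sentence could also be read at study level (the overall rate while dosing is generally compliant). Hence the limb concerns within-limit subjects most directly, not exclusively.

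**2. Provisions side by side.**

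| Provision | Dose condition | Subjects covered |
|---|---|---|
| 7.5, injury limb | dose kept | within limit |
| 4.3, toxicity assessment | dose exceeded | above limit |
| 5.3, AE row (footnote 3) | dose exceeded | above limit |
| 7.3.1, follow-up of kidney events | dose exceeded | above limit |
| 7.3.1, acute AEs | dose exceeded, on one reading | unclear |
| 7.3.1, AE definition and CTCAE grading | none | all |
| 4.5, 5.2, 5.3, 6.2, creatinine | none | all |
| 9.3 and 10.5, renal toxicity reports | none | all |
| 7.4.1, serious events | none | all |

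**3. Does the general follow-up sentence close the gap?** Section 7.3.1 also says: "All adverse events, as specified in section 7.3, will be followed up according to good medical practices". Section 7.3 in turn covers events "reported to Radiation Oncology discipline per study calendar, regardless of its relationship to study therapy, will be monitored until" they resolve, stabilise or are otherwise explained. Section 4.7 adds: "Only AEs reported to Radiation Oncology discipline per study calendar will be captured and assessed". All of this depends on what the calendar is. If it is the AE row of 5.3, footnote 3 applies and a within-limit rise is outside. If it is the whole table, a rise found at a scheduled creatinine draw is inside. The text does not settle it.

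**4. Renal data that will exist.** 14 subjects × 2 scheduled draws = 28 post-procedure values, with no dose condition.

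**5. Timing of the first draw.** The window runs from day 7 − 3 = 4 to day 7 + 7 = 14, which is 14 − 4 + 1 = 11 permitted days. Section 1.3 puts the usual peak at days 4 to 7, so 4 of the 11 days cover it and 7 of the 11 (days 8 to 14) come after it.

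**6. How often would the wording be tested?** The documents give no risk, so these are assumptions. If all 14 subjects stay within the limit, the chance of at least one kidney event is 1 − (1 − p)^14:

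| Assumed risk p | Chance of at least one event |
|---|---|
| 2% | 0.25 |
| 5% | 0.51 |
| 10% | 0.77 |
| 20% | 0.96 |

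This is the chance that the situation arises. It is not the chance that an injury is missed, because creatinine is scheduled in all 14.

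**The case against.** The best reply is that renal monitoring already runs from creatinine to interim report to toxicity review without a dose filter. This stands. It defeats the stronger reading that a reader might take from footnote 3, namely that kidney injury goes unmeasured in within-limit subjects or that 7.5 cannot be evaluated for them. A rate could be computed from the creatinine values; 7.5 simply does not say so.

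A second reply is that grading is not ruled out. The AE definition in 7.3.1 includes laboratory abnormalities of clinical importance, and its CTCAE grading has no dose condition. The text at the end of 7.4 has events that are not unanticipated problems logged and summarised for the IRB. Section 6.2 tells all patients to report symptoms, and 5.4 allows removal for toxicity at any time. This stands as well, so the documents do not support saying that a within-limit rise could never be graded or acted on. They leave unclear whether it is scheduled to be.

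Third, two of the four restrictions can be read differently. The acute-AE sentence may mean that only kidney events are followed once the dose is exceeded. The kidney follow-up sentence comes after a general one and may be additive. This is fair. Section 4.3 and footnote 3 are unambiguous and carry the point on assessment; the point on follow-up is less certain.

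Finally, a reader might measure the gap by counting the AE-assessment cells that footnote 3 leaves empty, or the subjects who would enter before a later review. Neither measures renal detection, and the second needs an accrual rate that the plan does not state.

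**Conclusion.** The mismatch is real but narrow. The injury limb of 7.5 is directed mainly at within-limit subjects, while 4.3 and footnote 3 schedule AE assessment only above the limit. The follow-up paragraph of 7.3.1, and on one reading its acute-AE paragraph, ties kidney follow-up to the same condition. The result is that a non-serious creatinine rise in a within-limit subject has no clearly scheduled AE assessment or kidney-AE follow-up. Section 9.3 nevertheless asks for severity, and 7.5 names no data source.

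This rests on reading the dose phrase in 7.5 as staying within the limit, which the second limb supports, and on most subjects staying within it, as 4.6 intends (4.3 and 7.1.2 let the radiologists exceed it). Serious injury would still reach the DSMC. The sample size and the primary Dice comparison are untouched. It is worth correcting because the correction is cheap, not because the trial is unsafe without it.

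**What to change.** - In 4.3, footnote 3 of 5.3, and the acute-AE and follow-up paragraphs of 7.3.1, remove the over-limit condition for kidney events. Keep contrast reactions monitored in all subjects, since 4.3 monitors allergic reactions with no dose condition in that sentence. Footnote 3 could read: *Kidney events and contrast reactions: all subjects. Other AEs: only subjects above the recommended contrast dose.*
- Reword 7.5 so that kidney injury is counted in every subject who receives both contrast studies, from the scheduled 1-week and 1-month creatinine values graded by CTCAE v5.0 against baseline. Make dose compliance a separate limb.

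The cost is wording in five places and grading up to 28 values that are already scheduled. Following a rise to resolution under 7.3 may occasionally need a draw after 1 month. Counting graded events in everyone may raise the chance of stopping; by how much cannot be said, because 7.5 has no threshold.

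Two limits remain. A first draw on days 8 to 14 may miss the usual peak, so the team should aim for the early part of the window. The rewording also does not supply an expected rate or a trigger number; the sponsor and DSMC should state both when they amend 7.5.

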8.0 DRUG INFORMATION

ISOVUE 300 and 370 ® are products of Bracco Diagnostics, Inc, Cranbury, NJ. Per the ISOVUE package insert, the maximum recommended dose of ISOVUE-370 for multiple procedures is 225 mL for adults and 125 mL for children between the ages of 10 to 18. ISOVUE is the brand currently used by UTSW hospitals. There are other vendors of iodinated contrast and UTSW's utilization may change.

9.0 STATISTICAL CONSIDERATIONS

9.1 Study Design/Study Endpoints

The primary endpoint of this study is to compare the target generated from interventional cerebral arteriography (reference) to targets generated from CT angiogram and MRI alone, to assess whether noninvasive imaging approaches are non-inferior to the UTSW standard.

